13.2 Antitumor Effect

13.2.1 Methods for Evaluation of Disease

All baseline evaluations should be performed on Cycle 1, Day 1 (Week 1) of initial therapy. Response will be assessed at each cycle, at the end of treatment visit, and every 3 months (follow up) thereafter. Response will be assessed by M-protein quantification, protein electrophoresis and immunofixation from serum and a 24-hour urine collection (unless participants are not measured for response in their urine), A serum sample for free light chain ratio testing will be obtained. In addition, bone marrow aspiration and biopsy, as well as skeletal survey/PET-CT/MRI will be performed to determine overall response or confirm response. Evaluations should be performed as determined by the Study Calendar, Section 10.

Daratumumab, as an immunoglobulin, may interfere with clinical SPE/IFE assessments. In cases where daratumumab interference is suspected, a reflex assay (DIRA: Daratumumab-specific Interference Reflex Assay) confirming the presence of daratumumab will be performed. In cases where CR or sCR is suspected and DIRA confirms that daratumumab is present on SPE/IFE, additional clinical assessments will be triggered to confirm the CR/sCR. A patient who meets all other clinical criteria for CR/sCR, and who has daratumumab interference confirmed by the reflex assay, will be considered a CR/sCR.

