1.4 Primary Objectives

- To determine the proportion of patients who are in VGPR or better after twenty cycles of therapy with Daratumumab. This will be determined at the time of best overall response.

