10. STUDY CALENDAR

Screening evaluations are to be conducted within 42 days prior to registration. Baseline assessments are to be conducted on C1D1 of initial therapy and should be considered separate from screening evaluations. If screening assessments are performed within 7 days of C1D1, disease assessments do not need to be repeated. All assessments must be performed prior to administration of any study medication. See below for detailed scheduled of assessments. Study medications will be administered according to the schedule and guidelines outlined in Section 5.

Tests and procedures	Pre-registration	During Treatment ^{1,3}			End of Treatment ¹³	Follow Up ¹⁸
	≤ 42 days prior to registration	Cycle 1-20 Day 1	Cycle 1-20 Intracycle on Days of Dosing	Clinically Indicated or to confirm CR ⁹		Every 3-6 Months ²²
History and exam, height, weight, vital signs. Performance Status	X	X			X	X
Toxicity Notation	X	X			X	
Hematology group (WBC w/ diff, PLT, Hgb, ANC) ^{1,10}	X	X	X		X	X
Chemistry ^{4, 10}	X	X	X		X	X
Direct & total bilirubin ^{2, 10}	X	X	X		X	
Blood Type and IAT Testing ¹⁴	X					

CONFIDENTIAL

This document is confidential. Do not disclose or use except as authorized.

HIV, HBV, HCV Testing ^{19,20}	X	X ²⁰			X ²⁰	X ²⁰
Free light chain assay ¹⁰	X	X			X	X
Serum and Urine Immunofixation (SPEP and UPEP) with quantitative immunoglobulins ^{10, 11}	X	X ⁸			X	X
Response Assessment ¹⁷		X			X	X
β2M, CRP, LDH ¹⁰	X	X	X		X	X
Metastatic Bone Survey and MRI of the Full Spine OR PET/CT ¹⁶	X				X	X
EKG	X				X	
PFT ²¹	X					
Serum or urine pregnancy test	X					
Unilateral bone marrow aspirate and biopsy ⁵	X			X	X	X ¹²
Research bone marrow aspirate ⁶	X ⁵			X ⁶	X ⁶	X ¹²
Research Blood ⁷	X ⁷	X ⁷		X ⁷	X ⁷	X
Research Buccal Swab ¹⁵	X					

- 1- Cycle 1, Day 1 hematologic laboratory values need to meet eligibility criteria to begin treatment
- 2- Direct bilirubin to be obtained if total bilirubin is abnormal.
- 3- Scheduling allows for -2/ +7 days.
- 4- Chemistry includes sodium, potassium, chloride, bicarbonate, blood urea nitrogen, creatinine, calcium, glucose, albumin, ALT (SGPT), total protein, AST (SGOT), total bilirubin, uric acid, alkaline phosphatase, magnesium, and phosphorus.
- 5- These procedures should also be done at any time during the course of the study to confirm CR, or as clinically indicated
- 6- Research bone marrow aspirate and biopsy at same time of clinically indicated bone marrow biopsy and to confirm response.

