- 7- Peripheral blood samples for correlative studies.
- 8- SPEP with immunofixation and quantitative immunoglobulins should be performed at screening, cycles 1-20 day 1, EOT, and at each follow-up visit.
- 9- If confirmation of response BM biopsy/aspirate was performed within 12 weeks of subsequent time point listed; the aspirate need only be repeated.
- 10- For Cycle 1 Day 1, no need to repeat tests if they have been performed within the past 7 days. Testing may be performed up to 2 days before other infusion days. Results of hematology tests must be evaluated before each study drug administration. Perform at additional timepoints, as clinically indicated. To be done by local lab. Patients need only meet hematologic inclusion criteria to begin treatment on C1D1.
- 11- If the participant's disease response is not followed primarily via a UPEP and Urine immunofixation, these tests may be done only at screening, as clinically indicated during treatment, end of treatment, and as clinically indicated during follow-up.
- 12- Strongly recommended to be performed yearly after EOT during follow-up and is required when there is suspected clinical progression
- 13- End of Treatment Assessments should be performed 4 weeks (+/- 1 week) after the last dose of daratumumab
- 14- Participants should receive blood typing card per section 3.3.1, prior to first dose of therapy- If the participating institution does not have a card that it provides its patients, refer to Appendix G for a template for completion by the study team and given to each participant
- 15- Buccal swab(s) may be collected at any time during the study
- 16- If PET/CT results are concerning for myeloma involvement, a follow up MRI must be conducted to confirm eligibility (baseline) or progression (on study and in follow up) PET CT strongly recommended yearly after EOT during follow up and are required at time of suspected disease progression.
- 17- A response assessment is required starting on C2D1, and at cycle thereafter based on Day 1 values, at EOT, and at each follow up Day 1 until off study.
- 18- If travel to the main site is financially burdensome on the participant, an alternate follow up schedule may be approved after discussion with the Overall PI- Window for follow up visits is +/- 4 weeks (28 days)

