13. MEASUREMENT OF EFFECT

13.1 Development of symptomatic disease

In this study, patients may continue on study until the development of symptomatic MM that requires therapy. This is defined as one of the following criteria (CRAB and Myeloma defining events < MDE):

- Increased calcium levels (corrected serum calcium >0.25 mmol/dL above the upper limit of normal or >0.275 mmol/dL) due to myeloma
- Renal insufficiency (attributable to myeloma);
- Anemia (Hb 2g/dL below the lower limit of normal or <10 g/dL) due to myeloma
- Bone lesions (lytic lesions or generalized osteoporosis with compression fractures)
- Or any MYELOMA DEFINING EVENTS (MDE) as follows:
 - Clonal bone marrow plasma cell percentage $\geq 60\%$ ²⁰
 - An abnormal FLC-ratio ≥ 100 (involved kappa) or <0.01 (involved lambda)²¹
 - >1 focal lesions (≥ 5 mm) on MRI or PET-CT studies^{22,23}

CONFIDENTIAL

This document is confidential. Do not disclose or use except as authorized.

For measurement of response:

The disease response will be assessed using criteria based on the International Working Group Uniform Response Criteria in Section 14.2.2.1. If the only measurable parameter is serum immunoglobulins free light chain (FLC), the participant will be followed by IMWG Response Criteria provided in Section 13.2.2.2

Disease response by the Modified EBMT Response Criteria in Section 13.2.2.3 will also be collected on participants as a secondary measure.

The same method of assessment and technique should be used for disease measurement at baseline and during follow-up. Disease response should be confirmed by two consecutive assessments.

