13.2.2.1 International Myeloma Working Group Response Criteria

Response criteria for all categories and subcategories of response except CR are applicable only to patients who have 'measurable' disease, as defined in Section 11.1.1 All response categories require two consecutive assessments made at any time before the institution of any new therapy; all categories also require no known evidence of progressive or new bone lesions if radiographic studies were performed. Radiographic studies are not required to satisfy these response requirements.

CONFIDENTIAL

This document is confidential. Do not disclose or use except as authorized.

Response	Criteria for Response
Stringent CR (sCR)	
CR as defined below plus normal free light chain ratio and absence of clonal cells in bone marrow* by immunohistochemistry or immunofluorescence.**
 
*Confirmation with repeat bone marrow biopsy is not needed.
 
**Presence/absence of clonal cells is based upon the k/λ ratio. An abnormal k/λ ratio by immunohistochemistry and/or immunofluorescence requires a minimum of 100 plasma cells for analysis. An abnormal ratio reflecting presence of an abnormal clone is k/λ of > 4:1 or < 1:2.

Complete Response (CR)	
Negative immunofixation on the serum and urine and disappearance of any soft tissue plasmacytomas and ≤5% plasma cells in bone marrow.
 
*Confirmation with repeat bone marrow biopsy is not needed.

Very Good Partial Response (VGPR)	
Serum and urine M-protein detectable by immunofixation but not on electrophoresis or 90% or greater reduction in serum M-protein plus urine M-protein level <100 mg per 24 hours.

Partial Response (PR)	
≥ 50% reduction of serum M-protein and reduction in 24-h urinary M-protein by ≥ 90% or to < 200 mg per 24 hours. If the serum and urine M-protein are unmeasurable, a ≥ 50% decrease in the difference between involved and uninvolved free light chain levels is required in place of the M-protein criteria (definition of measurable disease in Section 10.2.3). If serum and urine M-protein are unmeasurable, and serum free light assay is also unmeasurable, ≥ 50% reduction in plasma cells is required in place of M-protein, provided baseline bone marrow plasma cell percentage was ≥ 30%. In addition to the above listed criteria, if present at baseline, a > 50% reduction in the size of soft tissue plasmacytomas is also required.

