13.2.2.2 Modified EBMT Disease Response Criteria

Response	Criteria for Response ^a
Complete Response (CR)	
Requires all of the following:
 
Disappearance of the original monoclonal protein from the blood and urine on at least two determinations for a minimum of six weeks by immunofixation studies.
 
<5% plasma cells in the bone marrow on at least two determinations for a minimum of six weeks.^b
 
No increase in the size or number of lytic bone lesions (development of a compression fracture does not exclude response).^c
 
Disappearance of soft tissue plasmacytomas for at least six weeks.

Near Complete Response (nCR)	
Requires the following:
 
Same as CR, but immunofixation studies continue to show presence of the monoclonal protein

Very Good Partial Response (VGPR)	
Requires the following:
 
≥ 90% reduction in serum M-protein plus urine M-protein level <100mg per 24 hours on at least two determinations for a minimum of six weeks.

CONFIDENTIAL

This document is confidential. Do not disclose or use except as authorized.

Partial response (PR)
	
PR includes participants in whom some, but not all, criteria for CR are fulfilled providing the remaining criteria satisfy the requirements for PR. Required all of the following:
 
≥50% reduction in the level of serum monoclonal protein for at least two determinations six weeks apart.
 
If present, reduction in 24-hour urinary light chain excretion by either ≥90% or to < 200 mg for at least two determinations six weeks apart.
 
≥50% reduction in the size of soft tissue plasmacytomas (by clinical or radiographic examination) for at least six weeks.
 
No increase in size or number of lytic bone lesions (development of compression fracture does not exclude response).^c

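### Does the primary endpoint need a written VGPR coding rule for daratumumab interference, when the protocol gives one only for CR/sCR?

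*Combined protocol and SAP*

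**What the plan says.** Section 13.2.1 recognises that daratumumab, being an immunoglobulin, can disturb electrophoresis and immunofixation, and it orders the reflex assay whenever this is suspected, at any level of response. The follow-up steps concern complete response only: "In cases where CR or sCR is suspected and DIRA confirms that daratumumab is present on SPE/IFE, additional clinical assessments will be triggered", and a patient who meets the other criteria and "who has daratumumab interference confirmed by the reflex assay, will be considered a CR/sCR".

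The primary endpoint (Sections 1.4, 15.1 and 15.1.1) is the proportion with VGPR or better. Section 1.4 adds: "This will be determined at the time of best overall response". The IMWG VGPR row in Section 13.2.2.1 reads "Serum and urine M-protein detectable by immunofixation but not on electrophoresis or 90% or greater reduction in serum M-protein", with a limit on urine M-protein. It does not mention a drug band. Section 13.2.6 plans no central review of response.

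**The concern.** The one interference rule sits at CR/sCR, while pass or fail is decided between PR and VGPR. A patient whose own serum protein has gone, but who shows a daratumumab band and misses another CR criterion, gets no help from the CR rule. A literal reader could count the drug band as M-protein and score PR, while another site scores the same picture VGPR. With no central review, nothing in the text would settle the difference. A true deep responder scored PR lowers the observed rate, and the success rule can turn on a single patient.

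**Working it through.** **1. The plan's own figures.** Inputs from Section 15.1: n = 50, success at 32 or more, reference rate 50%, alternatives 70% and 75%. Exact binomial tails:

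- P(X ≥ 32 | 0.50) = 0.0325 (plan: 0.03)
- P(X ≥ 32 | 0.70) = 0.859 (plan: 86%)
- P(X ≥ 32 | 0.75) = 0.971 (plan: 97%)

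The exact two-sided 90% lower limit at x responders is the 5th percentile of Beta(x, 50 − x + 1). For x = 32, Beta(32, 19) gives 0.514. For x = 31, Beta(31, 20) gives 0.494. So 32 is the smallest passing count, and the design reproduces.

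**2. The two response rows compared (Section 13.2.2.1).** CR is written as a laboratory result: immunofixation must be negative. A drug band makes the test positive whatever its origin, so without an exception the patient fails. VGPR is written in terms of M-protein, either not visible on electrophoresis or reduced by at least 90%. If the assay shows that the serum band is infused antibody, the patient's own protein has gone and the 90% route is met without an exception, provided the urine limit also holds. This explains why the rule appears in one place and not the other.

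**3. What the plan does with a drug-only serum band.**

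- The assay is run, because interference is suspected.
- The patient is a suspected CR, so Section 13.2.1 triggers further assessment. Study Calendar note 5 covers the marrow: "These procedures should also be done at any time during the course of the study to confirm CR, or as clinically indicated". Marrow is also scheduled at end of treatment.
- If the other CR criteria are met, the patient is coded CR and counts towards the primary endpoint.
- If response is followed by free light chains alone, the clarification under the IMWG table scores VGPR on the light-chain difference, which does not use the serum band.
- The remainder is a patient who is assessed and fails CR elsewhere (for example, marrow plasma cells above 5%, or positive urine immunofixation) and whose site counts the confirmed drug band as M-protein.

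**4. Opportunities to be scored correctly.** Scoring is by best overall response. Section 13.2.2.1 accepts two consecutive assessments at any time before new therapy, and Study Calendar note 17 continues response assessment through follow-up, after the drug has stopped. During treatment, days from last dose to each pre-dose Day 1 assessment are:

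| Visits | Days since last dose | Number |
|---|---|---|
| C2–C3 | 7 | 2 |
| C4–C7 | 14 | 4 |
| C8–C20 | 28 | 13 |
| End of treatment | 28 ± 7 | 1 |

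That is 20 assessments, of which 14 fall nominally 28 days after a dose. For the last, note 13 says "End of Treatment Assessments should be performed 4 weeks (+/- 1 week) after the last dose of daratumumab". The documents do not say how large a drug band would be at any of these times.

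**5. Size if miscoding did occur (assumed numbers).** If k true deep responders are scored PR, success needs a true count of 32 + k:

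| k | True 50% | True 70% | True 75% |
|---|---|---|---|
| 0 | 0.0325 | 0.859 | 0.971 |
| 1 | 0.0164 | 0.782 | 0.945 |
| 2 | 0.0077 | 0.684 | 0.902 |

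One such patient reverses the result only at a true count of exactly 32: 0.8594 − 0.7822 = 0.077 at 70%, and 0.9713 − 0.9449 = 0.026 at 75%. If instead a share m of deep responders is lost, the observed rate is p(1 − m). For m = 2%, 5%, 10% and 15%, power is 80.5%, 70.4%, 50.5% and 31.0% at p = 70%, and 95.0%, 89.9%, 75.4% and 54.9% at p = 75%. Nothing in the documents supports any particular k or m.

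**6. The opposite error.** If a share f of patients without deep response were raised to VGPR by attributing a band to drug, the observed rate at a true 50% is 0.5 + 0.5f. For f = 2%, 5% and 10%, type I error rises from 0.032 to 0.044, 0.068 and 0.127.

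**The case for a change.** The strongest case for a written rule starts with eligibility. Under Section 3.1.2 an IgG patient with high-risk MGUS must have M-protein of at least 1.5 and below 3.0 g/dL, so a 90% reduction leaves 0.15 to just under 0.30 g/dL. At that level a small drug band could decide the category. Low-risk smoldering patients may enter with marrow plasma cells of 10% or more, so failing the 5% marrow condition is plausible. Response needs two consecutive assessments, so interference at either can block confirmation. The protocol nowhere defines M-protein as excluding drug. Source-document monitoring under Appendix D can detect discrepancies but supplies no definition.

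It stands that VGPR has no written rule and that the frequency is unknown. Two supporting arguments fall away. The EBMT criteria, which "will also be collected on participants as a secondary measure", do say "Disappearance of the original monoclonal protein from the blood and urine", but in their CR row. Their VGPR row says only serum M-protein, as the IMWG row does, so no contrast at VGPR can be drawn. Nor would a written rule clearly improve matters. Section 13.2.1 says the assay confirms that daratumumab is present; it does not say the assay shows a band to be drug alone. The CR rule guards against this by requiring every other criterion to be met. A VGPR rule without that guard risks the upward miscoding in step 6, which is the error that could create a false promising result.

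**Conclusion.** No change to the plan. The silence at VGPR is a missing definition that an assessor holding the reflex-assay result would fill sensibly, because the criterion concerns the patient's M-protein and nothing in the text tells sites to count drug as M-protein. The exposed group is narrow: a drug-only serum band, another CR criterion failed, response not followed by light chains alone, and a site that counts the drug band at every qualifying assessment. Its size cannot be derived from the documents and may be zero. With one such patient assumed, success falls from 86% to 78% at a true 70% and from 97% to 94% at 75%. Larger assumed shares cost more but have no source in the documents. Scoring deep responders as PR can only make the trial more conservative. The conclusion rests on the natural reading of M-protein and on counting follow-up assessments towards best response, which Section 13.2.2.1 supports although the reference in Section 1.4 to twenty cycles leaves some ambiguity. N, the 32/50 cut-off and the stated power are unaffected.

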13.2.2 Response Criteria

A confirmation measurement for disease response assessments is required in this protocol.

13.2.2.1 International Myeloma Working Group Response Criteria

Response criteria for all categories and subcategories of response except CR are applicable only to patients who have 'measurable' disease, as defined in Section 11.1.1 All response categories require two consecutive assessments made at any time before the institution of any new therapy; all categories also require no known evidence of progressive or new bone lesions if radiographic studies were performed. Radiographic studies are not required to satisfy these response requirements.

CONFIDENTIAL

This document is confidential. Do not disclose or use except as authorized.

Response	Criteria for Response
Stringent CR (sCR)	
CR as defined below plus normal free light chain ratio and absence of clonal cells in bone marrow* by immunohistochemistry or immunofluorescence.**
 
*Confirmation with repeat bone marrow biopsy is not needed.
 
**Presence/absence of clonal cells is based upon the k/λ ratio. An abnormal k/λ ratio by immunohistochemistry and/or immunofluorescence requires a minimum of 100 plasma cells for analysis. An abnormal ratio reflecting presence of an abnormal clone is k/λ of > 4:1 or < 1:2.

Complete Response (CR)	
Negative immunofixation on the serum and urine and disappearance of any soft tissue plasmacytomas and ≤5% plasma cells in bone marrow.
 
*Confirmation with repeat bone marrow biopsy is not needed.

Very Good Partial Response (VGPR)	
Serum and urine M-protein detectable by immunofixation but not on electrophoresis or 90% or greater reduction in serum M-protein plus urine M-protein level <100 mg per 24 hours.

Partial Response (PR)	
≥ 50% reduction of serum M-protein and reduction in 24-h urinary M-protein by ≥ 90% or to < 200 mg per 24 hours. If the serum and urine M-protein are unmeasurable, a ≥ 50% decrease in the difference between involved and uninvolved free light chain levels is required in place of the M-protein criteria (definition of measurable disease in Section 10.2.3). If serum and urine M-protein are unmeasurable, and serum free light assay is also unmeasurable, ≥ 50% reduction in plasma cells is required in place of M-protein, provided baseline bone marrow plasma cell percentage was ≥ 30%. In addition to the above listed criteria, if present at baseline, a > 50% reduction in the size of soft tissue plasmacytomas is also required.

Stable Disease (SD)	
Not meeting criteria for CR, VGPR, PR or progressive disease. This is not recommended as an indicator of response; stability of disease is best described by providing the time to progression estimates.

Progressive Disease (PD)	
> 25% increase of serum M-protein (which must also be an absolute increase of ≥ 0.5 g/dL) and/or urine M-protein (which must also be an absolute increase of ≥ 200 mg/24hr). If serum and urine M-protein are unmeasurable, there must be an absolute increase of ≥ 10 mg/dL between involved and uninvolved FLC levels. PD is also measured by an absolute increase in bone marrow plasma cells ≥ 10%. In addition to the above listed criteria, progression may also be measured by a definite development of new bone lesions or soft tissue plasmacytomas or definite increase in the size of existing bone lesions or soft tissue plasmacytomas or development of hypercalcemia (corrected serum calcium ≥ 11.5 mg/dL or 2.65 mmol/L) that can be attributed solely to the plasma cell proliferative disorder.

CONFIDENTIAL

This document is confidential. Do not disclose or use except as authorized.

*Clarifications to IMWG criteria for coding CR and VGPR in patients in whom the only measurable disease is by serum FLC levels: CR in such patients indicates a normal FLC ratio of 0.26 to 1.65 in addition to CR criteria listed above. VGPR in such patients requires a > 90% decrease in the difference between involved and uninvolved FLC levels.

†Clarifications for coding PD: Bone marrow criteria for PD are to be used only in patients without measurable disease by M protein and by FLC levels. The “25% increase” refers to M protein, FLC, and bone marrow results, and does not refer to bone lesions, soft tissue plasmacytomas, or hypercalcemia and the “lowest response value” does not need to be a confirmed value.

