2. BACKGROUND

2.1 Multiple Myeloma

Multiple myeloma is a plasma cell neoplasm characterized by multifocal proliferation of clonal, long-lived plasma cells associated with an overproduction of monoclonal gammaglobulin³¹. In 2010 the International Myeloma Working Group (IMWG) defined monoclonal gammopathy of undetermined significance (MGUS) by the presence of serum M-protein < 3 g/dL, clonal plasma cell population in the bone marrow < 10%, and the absence of end-organ damage such as hypercalcemia (serum calcium \geq 11 mg/dL), renal insufficiency (serum creatinine > 2 mg/dL), anemia (hemoglobin value below the lower limit of normal by more than 2 g/dL or hemoglobin value < 10 g/dL) and lytic bone lesions (CRAB features) that can be attributed to the plasma cell proliferative disorder³². Smoldering multiple myeloma was defined by the presence of serum M-protein \geq 3 g/dL or urinary monoclonal protein \geq 500 mg/dL and/or clonal bone marrow plasma cells 10-60% and the absence of CRAB features clinically.

In a large population based study in Olmsted County, MN, Kyle et al. analyzed serum samples of more than 75% of residents, 50 years or older, within the county³³. They identified MGUS in 694 of 21,463 patients tested (3.2%). While the overall prevalence was noted to be 3.2% (95 % CI, 3.0 to 3.5), there was a significant age dependent increase in both sexes with the prevalence among persons 80 years of age or older 4 times as high as among those 50-59 years of age. Age-adjusted rates were higher in men (4.0 %, 95% C.I., 3.5 to 4.4) than in women (2.7%, 95% C.I., 2.4 to 3.0). In a subsequent study on a majority of the same patients from Olmsted County, Dispenzieri, *et al*, used the free light chain assay (FREELITE) and showed that 0.8% of people older than 50 years had light chain-MGUS. The total MGUS prevalence including the light chain-MGUS cases was noted at 4.2% (95% C.I., 3.9 to 4.5%)³⁴. A limitation of both these studies was that 97.3% of the residents of Olmsted County were white.

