For SMM patients a M-protein \geq 3 g/dL, a FLC ratio outside the range of 0.125 to 8, and \geq 10% plasma cells in the bone marrow are considered as adverse factors in this model^{24,25}. The 5-year rate of progression in patients with 1, 2 and 3 risk factors was 25%, 51% and 76% respectively. The time to progression with these risk factors was 10, 5.1 and 1.9 years respectively. Recently Rajkumar et al have proposed that SMM with >60% plasma cells progress to multiple myeloma within 2 years in 95% cases and should be treated at diagnosis even in the absence of symptoms²⁰.

Table 1: Definitions currently available for MGUS and smoldering myeloma

International Myeloma Working Group criteria, 2010 version³²	
MGUS	
 ▪ Serum M protein <3 g/dL ▪ Clonal bone marrow plasma cells <10% ▪ Absence of myeloma defining events and amyloidosis
SMM	
 ▪ Serum M protein \geq3 g/dL ▪ and/or clonal bone marrow plasma cells 10% - 60% ▪ or urinary monoclonal protein \geq500 mg per 24 hours ▪ or FLC ratio < 0.125 or > 8 ▪ or \geq 95% abnormal plasma cells in the bone marrow ▪ or immunoparesis of one or more immunoglobulins ▪ Absence of myeloma defining events and amyloidosis
MM	
 ▪ Clonal bone marrow plasma cells \geq10% and/or biopsy proven plasmacytoma ▪ Presence of serum and/or urinary monoclonal protein at any level ▪ Evidence of end organ damage that can be attributed to the underlying plasma cell proliferative disorder (CRAB criteria) 
 ○ Hypercalcemia: Serum calcium >0.25 mmol/L above upper limit of normal or > 2.75 mmol/L (> 1 mg/dL above upper limit of normal) ○ Renal insufficiency: Serum creatinine > 173 μmol/L (>2 mg/dL) ○ Anemia: Normochromic, normocytic with a hemoglobin value of >2 g/dL below the lower limit of normal or a hemoglobin value <10 g/dL ○ Bone lesions: Lytic lesions, or osteoporosis with compression fractures ▪ Or any MYELOMA DEFINING EVENTS (MDE) as follows: 
 ○ Clonal bone marrow plasma cell percentage* > 60%²⁰ ○ An abnormal FLC-ratio \geq100 (involved kappa) or <0.01 (involved lambda)²¹>1 or more focal lesions on MRI or PET-CT studies(\geq^{22, 23}

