
Minimal response (MR)
	
MR included participants in whom some, but not all, criteria for PR were fulfilled, providing the remaining criteria satisfied the requirements for MR. Required all of the following:
 
≥25% to 49% reduction in the level of serum monoclonal protein for at least two determinations six weeks apart.
 
If present, a ≥50 to 89% reduction in 24-hour light chain excretion, which still exceeds 200 mg/24 h, for at least two determinations six weeks apart.
 
≥25-49% reduction in the size of plasmacytomas (by clinical or radiographic examination) for at least six weeks.
 
No increase in size or number of lytic bone lesions (development of compression fracture does not exclude response).^c

No change (NC)
	
Not meeting the criteria for MR or PD.

CONFIDENTIAL

This document is confidential. Do not disclose or use except as authorized.

Response	Criteria for Response ^a

Progressive disease (PD) (for participants not in CR)
	
Requires one or more of the following:
 
>25% increase^d in the level of serum monoclonal paraprotein, which must also be an absolute increase of at least 5 g/L and confirmed on a repeat investigation.
 
>25% increase^d in 24-hour urinary light chain excretion, which must also be an absolute increase of at least 200 mg/24 h and confirmed on a repeat investigation.
 
>25% increase^d in plasma cells in a bone marrow aspirate or on trephine biopsy, which must also be an absolute increase of at least 10%.
 
Definite increase in the size of existing lytic bone lesions or soft tissue plasmacytomas.
 
Development of new bone lesions or soft tissue plasmacytomas (not including compression fracture).
 
Development of hypercalcemia (corrected serum calcium >11.5 mg/dL or 2.8 mmol/L not attributable to any other cause).

Relapse from CR
	
Required at least one of the following:
 
Reappearance of serum or urinary paraprotein on immunofixation or routine electrophoresis confirmed by at least one follow-up and excluding oligoclonal immune reconstitution.
 
≥5% plasma cells in the bone marrow aspirate or biopsy.
 
Development of new lytic bone lesions or soft tissue plasmacytomas or definite increase in the size of residual bone lesions (not including compression fracture).
 
Development of hypercalcemia (corrected serum calcium >11.5 mg/dL or 2.8 mmol/L not attributable to any other cause)^e.

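### The IMWG progression row pairs 11.5 mg/dL of calcium with 2.65 mmol/L, which is 10.6 mg/dL, so the two printed hypercalcemia limits disagree

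*Combined protocol and SAP*

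**What the plan says.** Calcium limits appear in several places.

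- **Section 13.2.2.1, IMWG criteria, PD row:** "development of hypercalcemia (corrected serum calcium ≥ 11.5 mg/dL or 2.65 mmol/L", with the added condition that it be attributable solely to the plasma cell disorder.
- **Section 13.2.2.2, modified EBMT criteria, PD row:** "Development of hypercalcemia (corrected serum calcium >11.5 mg/dL or 2.8 mmol/L not attributable to any other cause". The Relapse-from-CR row uses the same figures. Section 13.1 says that EBMT response "will also be collected on participants as a secondary measure".
- **Section 2.1, Table 1, MM row:** "Hypercalcemia: Serum calcium >0.25 mmol/L above upper limit of normal or > 2.75 mmol/L (> 1 mg/dL above upper limit of normal". The text of Section 2.1 gives 11 mg/dL as the absolute calcium limit for end-organ damage.
- **Section 13.1, symptomatic disease:** "corrected serum calcium >0.25 mmol/dL above the upper limit of normal or >0.275 mmol/dL". Sections 2.5 (definitions) and 3.1.3 (eligibility) carry the same figures in mmol/dL.

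Progression ends duration of response and time to progression (Section 13.2.4) and PFS (Section 13.2.5). Section 13.2.6 plans no central review of response. Calcium is part of the chemistry panel in the study calendar, drawn through treatment, at end of treatment and in follow-up.

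**The concern.** A threshold printed in two units should give the same answer in either. Here one mg/dL figure, 11.5, has two different mmol/L partners, 2.65 in one table and 2.8 in the other, so at least one pair must be wrong before anything is converted. The figures are joined by a plain *or*. A literal reader could take them as alternatives and apply whichever is met first, while another reader would use only the unit the laboratory reports.

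At stake is the consistency of progression calls that rest on calcium, and so the end dates of duration of response, time to progression and PFS. With several institutions and no central response review, the written criterion is the main means of keeping these calls alike.

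**Working it through.** **Inputs**

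- IMWG PD row: 11.5 mg/dL and 2.65 mmol/L (Section 13.2.2.1).
- EBMT PD and Relapse-from-CR rows: 11.5 mg/dL and 2.8 mmol/L (Section 13.2.2.2).
- Table 1: 0.25 mmol/L paired with 1 mg/dL, and an absolute limit of 2.75 mmol/L.
- Section 2.1 text: 11 mg/dL.
- Assumption from outside the documents: molar mass of calcium 40.078 g/mol, used only as a cross-check.

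**Step 1. The protocol's own conversion.** Table 1 implies 1 / 0.25 = 4.0 mg/dL per mmol/L. On that factor 11 / 4.0 = 2.75 mmol/L, so the text of Section 2.1 and Table 1 agree. Molar mass gives 40.078 / 10 = 4.008 mg/dL per mmol/L, practically the same.

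**Step 2. The figures in the response tables.**

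| Printed | Factor 4.0 | Factor 4.008 |
|---|---|---|
| 11.5 mg/dL | 2.875 mmol/L | 2.869 mmol/L |
| 2.65 mmol/L | 10.60 mg/dL | 10.62 mg/dL |
| 2.8 mmol/L | 11.20 mg/dL | 11.22 mg/dL |

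Neither pair reproduces. Rounding does not rescue them: 11.45 to 11.55 mg/dL is 2.857 to 2.882 mmol/L, which rounds to 2.9 at one decimal, never to 2.8 or 2.65. Cutting 2.87 off after one decimal would give 2.8. Nothing of that kind gives 2.65.

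**Step 3. Size of the gaps (factor 4.0).**

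- IMWG: 11.5 − 10.6 = 0.9 mg/dL; 0.9 / 11.5 = 7.8%.
- EBMT: 11.5 − 11.2 = 0.3 mg/dL; 0.3 / 11.5 = 2.6%.

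Example: 2.70 mmol/L is 2.70 × 4.0 = 10.8 mg/dL. If attributed solely to the plasma cell disorder, it is PD by the mmol/L figure in the IMWG row and not by the mg/dL figure.

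**Step 4. The mmol/dL limits in Sections 2.5, 3.1.3 and 13.1.** Since 1 mmol/dL = 10 mmol/L:

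- Absolute limb: 0.275 mmol/dL = 2.75 mmol/L = 11 mg/dL. This agrees with Table 1.
- Limb relative to the upper limit of normal (ULN): 0.25 mmol/dL = 2.5 mmol/L = 10 mg/dL above ULN. Table 1 has 0.25 mmol/L (1 mg/dL) above ULN, ten times smaller.

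As printed, the relative limb needs calcium above ULN + 2.5 mmol/L. The absolute limb at 2.75 mmol/L is reached first for any ULN above 0.25 mmol/L, that is, in any laboratory. The relative limb is therefore redundant. With Table 1's 0.25 mmol/L it would be reached first only where the ULN is below 2.50 mmol/L, and would matter only for values between ULN + 0.25 and 2.75 mmol/L. The documents give no ULN.

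**The case against.** The case for leaving this alone is mainly one of consequence, and much of it stands. Isolated hypercalcemia is one of several routes to PD and must be attributed solely to the plasma cell disorder. Section 8.4 requires scans and marrow at suspected progression, and Appendix D provides for source documents supporting the endpoints to be collected and allows response assessments to be monitored. Eligibility chemistry with a concentration unit is stated in mg/dL, and the supply plan refers to US sites, so the mmol/L figures may never be used. The EBMT table is secondary, and Section 15 plans no analysis on it. PFS is to be captured but is not a listed objective. Both tables are presented as published criteria, so a transcription slip cannot be told from a faithful copy. None of this makes the printed pairs equivalent.

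Three stronger inferences should be resisted.

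- **That a patient could have hypercalcemia PD without hypercalcemia**, because 2.65 lies below Table 1's 2.75 mmol/L. Table 1 sets a limit for overt myeloma and also has a ULN-relative limb, which a value of 2.65 meets if the ULN is below 2.40 mmol/L. A progression limit below the overt-myeloma limit is not itself an error either: M-protein progression also falls short of overt myeloma, and Section 8.4 separates biochemical progression from symptomatic disease.
- **That Section 13.1 would let symptomatic hypercalcemia go unrecognised.** Its absolute limb still operates at 2.75 mmol/L.
- **That the primary result is at risk.** Calcium is not part of the VGPR definition or of the 32-of-50 rule.

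**Conclusion.** The point holds as a wrong figure in a decision threshold with a small expected effect. The clear defect is the IMWG PD row, where the two printed limits differ by 0.9 mg/dL (about 8%) and values from 10.6 to just under 11.5 mg/dL are classified differently. The EBMT mismatch is minor (0.3 mg/dL, about 2.5%) and confined to a secondary measure. The ULN-relative limit in mmol/dL is a separate unit fault that makes that limb redundant; the absolute limit beside it is numerically sound.

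The arithmetic rests on the protocol's own 4.0 factor, and molar mass gives the same conclusion. It shows that the pairs disagree, not which figure is intended. The effect is limited to PD events resting on calcium alone, and arises only where the mmol/L figure is read; the documents do not state reporting units. Duration of response, time to progression and PFS are the outcomes that could move.

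**What to change.** 1. **Response tables.** The sponsor should confirm the intended threshold in each row and make the two figures equivalent, in the IMWG PD row and in both the PD and Relapse-from-CR rows of the EBMT table. For reference, 11.5 mg/dL corresponds to 2.87 mmol/L, 2.65 mmol/L to 10.6 mg/dL, and 2.8 mmol/L to 11.2 mg/dL. Which value is meant is for the sponsor to decide.
2. **Sections 2.5, 3.1.3 and 13.1.** Reconcile the calcium limits with Table 1, changing number and unit together. Relabelling the unit alone would be unsafe: 0.275 mmol/dL is 2.75 mmol/L, and writing it as 0.275 mmol/L would set a limit that every patient exceeds.

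The cost is a text correction. No design, sample-size or analysis change follows.
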